Week 12 CDAI was 190 and the hs-CRP obtained at Week 12 visit was 7 mg/L. The subject returns 2 weeks later and the CDAI at Week 14 is 220. The hs-CRP obtained at Week 12 should first be assessed with the Week 12 CDAI to determine if the inadequate response criteria have been met; which in this case does not meet criteria for dose escalation. Then the hs-CRP obtained at Week 12 should be assessed with Week 14 CDAI, which does meet the criteria for dose escalation; because the latter assessment met the criteria, the subject is eligible for dose escalation.

Laboratory Tests

Blood samples will be obtained for the laboratory tests listed in [Table 3](#) at the visits described in [Table 1](#). Blood draws should be performed after all clinical assessments and questionnaires (CDAI, IBDQ), vital sign determinations are obtained and before study drug administration during a visit, whenever possible.

A certified central laboratory will be utilized to process and provide results for the clinical laboratory tests. All abnormal laboratory tests that are considered clinically significant by the investigator will be followed to a satisfactory resolution.

The central laboratory chosen for this study will provide instructions regarding the collection, processing and shipping of these samples.

Table 3. Clinical Laboratory Tests

Hematology	Clinical Chemistry	Urinalysis	Other	Pregnancy Test
Hematocrit	Blood Urea Nitrogen (BUN)	Specific gravity	hs-CRP	Serum HCG
Hemoglobin	Creatinine	Ketones	C. difficile toxin	Urine (testing to be performed locally by designated study personnel)
Red Blood Cell (RBC) count	Total bilirubin	pH	Fecal calprotectin	
White Blood Cell (WBC) count	Serum glutamic-pyruvic transaminase (SGPT/ALT)	Protein	Antinuclear antibody (ANA)	
Neutrophils	Serum glutamic-oxaloacetic transaminase (SGOT/AST)	Blood	Anti-double-stranded DNA (anti-dsDNA) – if ANA positive	
Bands	Alkaline phosphatase	Glucose	HBs Ag	
Lymphocytes	Sodium		HBs Ab	
Monocytes	Potassium		HBe Ag	
Basophils	Calcium		HBe Ab	
Eosinophils	Inorganic phosphorus		HBc Ab Total	
Platelet count (estimate not acceptable)	Uric acid		PCR DNA (if needed)	
	Cholesterol		Pharmacokinetic	
	Total protein		HACA	
	Glucose		Infliximab	
	Triglycerides		Pharmacogenetic (optional)	
	Albumin		mRNA (optional)	
			HCV	
			HIV (testing to be conducted at central lab)	
			QuantiFERON-TB	
			Gold In-Tube	

Hepatitis and HIV Testing

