4.2 Design Diagram

This is a Phase 3, randomized, double-blind, placebo controlled, multicenter study of adalimumab in anti-TNF naïve Chinese subjects with moderately to severely active CD ($220 \leq \text{CDAI} \leq 450$) and elevated hs-CRP ($\geq 3 \text{ mg/L}$). The study consists of an 8-week DB period followed by an OL period of 18 weeks. Subjects will be randomized in a 1:1 ratio to receive adalimumab or placebo at Baseline. Subjects randomized to adalimumab at Week 0 will receive blinded adalimumab 160 mg at Week 0, 80 mg at Week 2, and 40 mg at Week 4 and Week 6. Subjects randomized to placebo at Week 0 will receive blinded placebo at Week 0 and Week 2, then will receive blinded adalimumab 160 mg at Week 4 and 80 mg at Week 6. At Week 8, all subjects will enroll in an 18-week OL period to receive adalimumab 40 mg every other week (eow). No drug will be administered at the final study visit.

The study was designed to enroll approximately 200 subjects to meet scientific and regulatory objectives without enrolling an undue number of subjects in alignment with ethical considerations.

[figure not shown]
The study duration will be up to 39 weeks, and will include a screening period of up to 35 days, an 8-week double blind treatment period, an 18-week OL period and a 70-day follow-up period. All subjects will have a follow-up phone call approximately 70 days after the last administration of study drug to obtain information on any new or ongoing AEs. The 70-day follow-up phone call will not be required for any subject who initiates adalimumab therapy not supplied in the context of Study M14-233 after the end of study participation.

At or after Week 12, any subject who experiences inadequate response may increase dose to OL adalimumab 80 mg eow. If the subject has received OL 80 mg eow therapy and continues to demonstrate inadequate response, he or she should be withdrawn from the study per PI discretion.

Subjects may discontinue adalimumab treatment at any time during study participation. Subjects who end study participation early will have a Premature Discontinuation Visit.

A schematic of the study design is shown in [Figure 1](#).

Figure 1. Study Design

The study activities are presented in [Table 1](#).

Table 1. Study Activities

Activity	Screening (35 Days)	Day -21 ^a	Day -7 ^a	Baseline (Wk 0) ^b	Wk 2	Wk 4	Wk 6	Wk 8	Wk 10	Wk 12	Wk 14	Wk 16	Wk 18	Wk 20	Wk 22	Wk 24	Wk 26/ Premature Discontinuation	Unscheduled Visit	70-Day Follow-Up Call ^c

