6.0 Analysis Conventions

Definition of Baseline

The Baseline Visit date is the date when the first dose of study drug is received and referred to as Day 1 or Week 0. The baseline value for a variable is defined as the last non-missing value on or before the date of the first dose of study drug.

When analyzing laboratory parameters and vital signs on the Any Adalimumab analysis set, the Baseline Visit date is the date when the first dose of adalimumab is received and will be counted as Day 1 or Week 0. The baseline value for a laboratory or vital sign measurement is defined as the last non-missing value on or before the date of the first dose of adalimumab.

Definition of Final Observation

Final observation in the 4-week DB placebo controlled treatment period is defined as the last non-missing observation collected within 70 days following the last dose of study drug or the date subjects initiate adalimumab therapy not supplied in the context of Study M14-233 for subjects who discontinue the study before Week 6, and on or before the day of the first dose of study drug at Week 6 for subjects who continues the study.

Final observation in the DB/OL period for the Any Adalimumab set is defined as the last non-missing observation collected within 70 days following the last dose of study drug, or the date subjects initiate adalimumab therapy not supplied in the context of Study M14-233.

Definition of Rx Days (Days Relative to the First Dose of Study Drug)

Rx Days are calculated for each time point of interest and provide a quantitative measure of days between the event and Day 1 (which can be the day of the first dose of study drug or the day of the first dose of adalimumab, depending on the analysis). That is, the Rx Day is calculated as the event date minus Day 1 plus 1. The Rx Day will be a negative value when the time point of interest is prior to Day 1, and the Rx Day will be a positive

value when the time point of interest is after Day 1. By this calculation algorithm, the first dose day is Rx Day 1, while the day prior to the date of first dose is defined as Rx Day –1 (there is no Rx Day 0). Rx Days are used to map actual study visits to the protocol-specified study visits.

Definition of Analysis Windows

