11.0 Safety Analysis

11.1 General Considerations

Safety analyses will include reporting of adverse events, laboratory, and vital sign measurements. Safety analyses will be carried out using the Safety set for the DB placebo controlled period (Week 0 to Week 4), and will be carried out using the Any Adalimumab set for the DB/OL period of Any Adalimumab (the entire study on or after the first dose of adalimumab up to 70 days after the last dose of adalimumab, or the date subjects initiate adalimumab therapy not supplied in the context of Study M14-233). The safety analyses results through Week 4 will be presented using two treatment groups (i.e., ADA160/80 versus placebo). The safety analysis on the Any Adalimumab set will be presented for all the subjects as one adalimumab treatment group.

Comparisons between active treatment and placebo groups will be performed for the DB placebo controlled period using the safety analysis set. The safety variable will be summarized by treatment according to the treatment a subject actually received. The differences between treatment group and placebo in safety parameters will be evaluated using two-sided tests at the significance level of 0.100.

For the any adalimumab analysis Set, only summary statistics will be provided for adalimumab treatment.

Missing safety data will not be imputed.

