11.2 Analysis of Adverse Events

11.2.1 Treatment-Emergent Adverse Events

Treatment-emergent AEs will be summarized separately for the DB placebo-controlled period and for the DB/OL period of Any Adalimumab.

Treatment-emergent AEs during placebo-controlled DB period are defined as events that begin or worsen either on or after the first dose of study drug and up to the first dose of

study drug at Week 4, or within 70 days after the last dose of study drug, or the date subjects initiate adalimumab therapy not supplied in the context of Study M14-233, for subjects who discontinued prior to Week 4. Treatment-emergent AEs during DB/OL period of Any Adalimumab are defined as events that begin or worsen either on or after the first dose of adalimumab in DB or OL period, and within 70 days after the last dose of study drug, or the date subjects initiate adalimumab therapy not supplied in the context of Study M14-233.

An overview of treatment-emergent AEs, including AEs of special interest such as adverse events leading to death and adverse events leading to early termination, AEs by Medical Dictionary for Drug Regulatory Activities (MedDRA version 20.0 or later) preferred term and system organ class, AEs by maximum relationship to study drug, and AEs by maximum severity will be summarized by number and percentage.

The number and percent of subjects experiencing treatment-emergent adverse events will be summarized for the following adverse event categories. Comparisons of the percent of subjects experiencing an adverse event between adalimumab and placebo during the DB placebo controlled period will be performed using Fisher's exact tests. Only P values < 0.100 when rounded to three digits will be presented.

- Any treatment-emergent adverse event.
- Any treatment-emergent adverse event with a Reasonable Possibility of being related to study drug by the investigator.
- Any treatment-emergent severe adverse event.
- Any treatment-emergent serious adverse event.
- Any treatment-emergent adverse event leading to discontinuation of study drug.
- Any treatment-emergent adverse event leading to death.
- Any treatment-emergent adverse event of special interest.
- Any deaths.

Adverse events with missing or unknown relationship to study drug will be categorized as having a reasonable possibility of being study drug-related. Adverse events with missing or unknown severity will be categorized as severe.

Treatment-emergent adverse events will be summarized as follows:

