11.2.2 Adverse Events of Special Interest

The following AEs of special interest will be summarized by number and percentage of subjects experiencing an AE of interest. The AEs of interest will be summarized and presented using primary MedDRA system organ classes (SOCs) and preferred terms (PTs) for the following AE categories:

- Any infection,
- Any serious infection,
- Any legionella infection,
- Any diverticulitis,
- Any opportunistic infection excluding oral candidiasis and TB,
- Any oral candidiasis,
- Any tuberculosis,
- Any active tuberculosis,

- Any latent tuberculosis,
- Any parasitic infection,
- Any reactivation of hepatitis B,
- Any progressive multifocal leukoencephalopathy (PML),
- Any malignancy,
- Any lymphoma,
- Any hepatosplenic T-cell lymphoma (HSTCL),
- Any non-melanoma skin cancers (NMSC),
- Any melanoma,
- Any leukaemia,
- Any malignancy other than lymphoma, HSTCL, leukaemia, NMSC or melanoma,
- Any allergic reaction including angioedema/anaphylaxis,
- Any lupus-like reactions and systemic lupus erythematosus,
- Any vasculitis,
- Any cutaneous vasculitis,
- Any non-cutaneous vasculitis,
- Any sarcoidosis,
- Any autoimmune hepatitis,
- Any myocardial infarction,
- Any cerebrovascular accident,
- Any CHF,
- Any pulmonary embolism,
- Any interstitial lung disease,
- Any intestinal perforation,
- Any intestinal stricture,
- Any pancreatitis,
- Any Stevens-Johnson Syndrome,
- Any erythema multiforme,

- Any worsening/new onset of psoriasis,
- Any demyelinating disorder,
- Any amyotrophic lateral sclerosis,
- Any reversible posterior leukoencephalopathy syndrome (RPLS),
- Any hematologic disorders including pancytopenia,
- Any liver failure and other liver event,
- Any Humira administration related medication error,
- Any injection site reaction.

Additional AEs may be considered for tabulation/summary based on recommendations from Clinical and Safety as deemed appropriate.

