11.3 Analysis of Laboratory Data

Changes from baseline in continuous laboratory parameters will be summarized for each visit. The mean change from baseline will be compared between treatment groups (ADA 160/80 versus placebo) at each time point during the DB placebo-controlled period on the Safety Analysis set. Summaries of mean changes from baseline will be provided on the Any Adalimumab set for the adalimumab treatment.

Mean changes from baseline to post-baseline visits will be summarized with the baseline mean, the visit mean, change from baseline mean, standard deviation and median. The treatment group differences for mean changes from baseline will be analyzed using a one-way ANOVA and between group mean change from baseline with the 95% confidence interval, standard error, and *P* value will be presented.

Shift tables from baseline to the final value according to the normal range will be provided for each hematology, clinical chemistry parameter and urinalysis parameter (specific gravity and pH only).

For selected laboratory parameter with Common Toxicity Criteria (CTC), frequencies and percentages of subjects with post baseline lab values that are Grade 3 or above according

to the CTC toxicity criteria Version 3.0 (or later) will be summarized. Comparisons of the percentage of subjects experiencing a value meeting the criteria between treatment groups will be performed using Fisher's exact tests. Only P values ≤ 0.100 when rounded to three digits will be presented. A separate listing will be provided that presents all of the subjects and values that are CTC toxicity Grade 3 or above. For each of these subjects, the whole course of the respective parameter will be listed.

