11.3.1 Analysis of Liver Specific Laboratory Tests

The liver specific laboratory tests include the serum glutamic-pyruvic transaminase (ALT/SGPT), serum glutamic-oxaloacetic transaminase (AST/SGOT), alkaline phosphatase and total bilirubin. Each of these laboratory values will be categorized as follows:

1. $< 1.5 \times \text{ULN}$,
2. $\geq 1.5 \times \text{ULN}$ TO $< 3 \times \text{ULN}$,
3. $\geq 3 \times \text{ULN}$ TO $< 5 \times \text{ULN}$,
4. $\geq 5 \times \text{ULN}$ TO $< 8 \times \text{ULN}$, and
5. $\geq 8 \times \text{ULN}$,

where ULN is the upper normal limit.

Shift tables showing shift from Baseline to maximum and final values will be presented using these five categories.

A listing of potentially clinically significant liver function laboratory values will be provided. The listing will include all subjects who met any of the following 4 criteria:

1. $\text{ALT} \geq 2.5 \times \text{ULN}$, or
2. $\text{AST} \geq 2.5 \times \text{ULN}$, or
3. Alkaline Phosphatase $\geq 2.5 \times \text{ULN}$, or

4. Total Bilirubin $\geq 1.5 \times$ ULN.

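### SAP 6.0 lets the final value of the 4-week placebo-controlled period run to the Week 6 dose, so placebo-arm laboratory shift tables can end on values taken about two weeks after adalimumab 160 mg

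*SAP*

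**What the plan says.** SAP 11.3 plans one kind of shift table for each hematology and chemistry parameter: "Shift tables from baseline to the final value according to the normal range will be provided". For ALT, AST, alkaline phosphatase and total bilirubin, SAP 11.3.1 adds: "Shift tables showing shift from Baseline to maximum and final values will be presented using these five categories".

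The SAP defines a final observation once, in section 6.0. For the period it calls the 4-week double-blind placebo-controlled period there are two branches. Subjects who stop before Week 6 contribute their last value up to 70 days after their last dose, or up to the start of non-study adalimumab. The others contribute the last value "on or before the day of the first dose of study drug at Week 6 for subjects who continues the study".

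Elsewhere the same period ends at Week 4:

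- SAP 9.0 measures exposure in the placebo-controlled period up to the date of the Week 4 injection.
- SAP 11.1: "Safety analyses will be carried out using the Safety set for the DB placebo controlled period (Week 0 to Week 4".
- SAP 11.2.1 counts treatment-emergent events up to the first dose of "study drug at Week 4, or within 70 days after the last dose of study drug" for subjects who stopped before Week 4.
- SAP 12.1 departs from the protocol's Week 0 to 8 safety period because placebo subjects receive adalimumab induction from Week 4.

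On dosing, SAP 4.2 says that placebo subjects "then will receive blinded adalimumab 160 mg at Week 4 and 80 mg at Week 6".

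**The concern.** The placebo-controlled shift tables are the only ones with a comparator, because the Any Adalimumab set is summarized as a single group. If the final value in them may come from Week 6, the placebo column mixes in subjects who already have two weeks of adalimumab induction. The contrast is then no longer adalimumab against placebo. A drug-related shift could be diluted, or one caused by the Week 4 dose could be counted under placebo.

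A second, smaller matter is that a final-value shift shows the last state only. A subject who is normal at baseline, abnormal at an intermediate visit and normal again at the end falls in the normal-to-normal cell. The four liver tests also get a shift to the maximum; hematology and the other chemistry parameters do not.

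**Working it through.** There is no planned figure to reproduce. The check compares the texts and counts days, visits and parameters.

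**1. Is there a Week 6 sample to pick up?** Hematology and chemistry are marked at Week 6 in Protocol Table 1. The hematocrit table in Protocol 5.3.1.1 uses the Week 6 value for the Week 8 CDAI. SAP Table 3 has a Week 6 window (Days 37 to 50). The protocol synopsis lists Weeks 0, 2, 4 and 8 only. Three of four sources therefore include Week 6. Protocol 5.3.1.1 asks for blood to be drawn before dosing where possible, so a Week 6 sample taken on the dosing day meets the SAP 6.0 rule. Urinalysis is not scheduled at Week 6, so its shift tables should be unaffected.

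**2. How long after adalimumab?** Nominal days are 29 (Week 4) and 43 (Week 6), and visits may move by 3 days either way.

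- Nominal: 43 − 29 = 14 days.
- Shortest: (43 − 3) − (29 + 3) = 40 − 32 = 8 days.
- Longest: (43 + 3) − (29 − 3) = 46 − 26 = 20 days.

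**3. Who and what is affected?** Every placebo subject who continues and has a Week 6 sample, up to the 100 planned. Protocol Table 3 lists 11 hematology and 16 chemistry parameters (four of them the liver tests): 11 + 16 = 27.

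**4. The same value is used twice.** In the Any Adalimumab set, day 1 for a placebo-start subject is the Week 4 dose. The Week 6 sample then falls nominally on day 43 − 29 + 1 = 15, inside the Week 2 window (Days 2 to 22) of SAP Table 7. One sample would be both a placebo final value and an on-adalimumab value.

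**5. The discontinuation branch has the same flaw.** A placebo subject who takes the Week 4 adalimumab dose and stops before Week 6 is allowed a placebo-period final value up to 70 days after that dose.

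**6. Final against worst value.** Scheduled post-baseline hematology and chemistry visits are Weeks 2, 4, 6, 8, 12, 16, 20 and 26, so 8 in all, of which 2 fall in Weeks 0 to 4. A final-value shift uses one value per subject per period. The price of a worst-value shift is chance findings. Assume a 2.5% tail in one direction at each visit, a baseline value not in that tail, jointly normal values with equal within-subject correlation, and no drug effect. The chance of at least one shift is:

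| Correlation | 1 value (final) | 2 visits (Weeks 2, 4) | 8 visits |
|---|---|---|---|
| 0 | 2.5% | 4.9% | 18.3% |
| 0.5 | 2.1% | 3.9% | 11.3% |
| 0.8 | 1.4% | 2.5% | 5.9% |

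Check at correlation 0: 1 − 0.975² = 4.9% and 1 − 0.975⁸ = 18.3%. The correlations are assumptions; the documents give none.

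**The case against.** **On the cut-off.** Section 6.0 itself calls the period 4-week, and four other sections end it at Week 4, so Week 6 looks like a drafting slip that a programmer might correct unprompted. The shift tables in 11.3 say final value, not final observation, so the link is an inference. No test is specified for these tables. All of this is fair and keeps the point minor. But the shift tables are the only analyses that call for a final value, so the definition has no evident use if it does not govern them. SAP 3.0 presents the conventions as guidance for programming, and a specific rule is likely to be coded as written.

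A reader might go further and infer that the between-arm laboratory comparison as a whole is compromised, or that an arm difference will be hidden. The documents do not support that. Mean changes are compared visit by visit, and those at Weeks 2 and 4 do not use the final-observation rule. Adverse events are cut off at Week 4. The direction and size of any distortion in the shift tables are unknown.

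**On worst values.** A reader might also infer that using final values is an error that loses transient abnormalities from the safety report. That is too strong. A final-value shift is a legitimate summary of the last state, and several other outputs sit beside it:

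- SAP 11.3 adds by-visit changes, any-time counts of CTC Grade 3 or above in selected parameters, and a listing with the whole course for those subjects.
- Under Protocol 6.1.1.1 a laboratory abnormality is an adverse event if it leads to discontinuation, needs treatment, meets protocol criteria or is judged one by the investigator. SAP 11.2.2 tabulates "Any hematologic disorders including pancytopenia".
- Protocol 8.1.5 promises listings of abnormal values, and SAP 12.1 does not withdraw them.
- Protocol 5.3.1.1 adds that "All abnormal laboratory tests that are considered clinically significant by the investigator will be followed to a satisfactory resolution"; this is care rather than a count.

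What remains is a missing count of resolved abnormalities that are below Grade 3, or in an unselected parameter, and were not reported as adverse events. The SAP 6.0 sentence that all values will be considered for shift summaries follows the same-day averaging rule and most naturally lifts that averaging; it does not set up a worst-value table. The liver table is not an exact model either: it looks upward only, in multiples of the upper limit of normal.

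**Conclusion.** The Week 6 cut-off in SAP 6.0 is wrong as written. It contradicts the label of its own period, SAP 9.0, 11.1 and 11.2.1, and the sponsor's rationale in 12.1. Followed literally, it replaces placebo final values with values taken about 14 days after adalimumab 160 mg in the hematology, chemistry and liver shift tables. This rests on two conditions: that final value in 11.3 and 11.3.1 means the final observation of 6.0, and that blood is drawn at Week 6 as Protocol Table 1 and SAP Table 3 state. Severity is minor, since the tables are descriptive and neither efficacy inference nor subject protection depends on them.

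The lack of a worst-value shift is not an error. How often abnormalities appear and resolve is not in the documents, so the value of adding one cannot be sized; its chance-finding cost can be, under the stated assumptions.

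**What to change.** **Correct the cut-off.** In the SAP 6.0 definition for the placebo-controlled period, replace Week 6 with Week 4 in both places: the branch for subjects who stop early and the branch for those who continue. State in 11.3 and 11.3.1 that final value means this final observation, and apply the same cut-off to the liver maximum, so that placebo-controlled values end on or before the day of the Week 4 dose for continuing subjects. The Week 6 sample stays in the Any Adalimumab set. This is a wording change and needs no new data.

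**Optional.** Next to the final-value shift, add a baseline-to-worst shift for WBC, neutrophils, lymphocytes, platelets and hemoglobin (minimum) and creatinine (maximum). Say that it is read mainly in the Week 0 to 4 between-arm comparison, where chance shifts are expected in both arms. The cost is tables for six parameters and more chance out-of-range shifts: 2.5% to 4.9% of subjects over two visits, against 1.4% to 2.5% for the final value, under the assumptions above. Over 8 visits without a comparator the figure is 5.9% to 18.3%, so a table of that kind on the Any Adalimumab set would need cautious reading.

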14. Previous participation in an adalimumab clinical study. Prior exposure to any anti-tumor necrosis factor (TNF) agent (including but not limited to branded or biosimilar versions of adalimumab [Humira[®]], infliximab [Remicade[®]], etanercept [Enbrel[®]], golimumab [Simponi[®]] or certolizumab pegol [Cimzia[®]]). Prior exposure to ustekinumab (Stelara[®]), tofacitinib (Xeljanz[®]), tocilizumab (Actemra[®]), anakinra (Kineret[®]), abatacept (Orencia[®]) or vedolizumab (Entyvio[®]).
15. Subject taking Crohn's-related antibiotics who has been on this therapy to treat an active infection or who has not been on stable doses of these medications for at least 14 days prior to Baseline.
16. Subject has received cyclosporine, tacrolimus, or mycophenolate mofetil within 30 days prior to Baseline (Week 0).
17. Active infection(s) requiring treatment with intravenous (IV) anti-infectives within 30 days prior to the Baseline (Week 0) Visit or oral anti-infectives within 14 days prior to the Baseline Visit.
18. Subject currently receiving total parenteral nutrition (TPN) during Screening and/or at Baseline (Week 0) or subject who plans to receive TPN at any time during the course of the study.
19. Subject with positive Clostridium difficile (*C. difficile*) toxin stool assay during the Screening period.
20. Subject has received any systemic traditional Chinese medicine preparation within 14 days before Baseline (Week 0).
21. Subject has received any thalidomide within 28 days before Baseline (Week 0).

22. Screening laboratory and other analyses show any of the following abnormal results (if a subject starts TB prophylaxis, lab results [except ECG] should be confirmed at Day -7):
- AST, ALT > 1.5 × upper limit of the reference range;
 - WBC count < 3.0 × 10⁹/L;
 - Electrocardiogram (ECG) – with clinically significant abnormalities;
 - Total bilirubin ≥ 3 mg/dL; except for subjects with isolated elevation of indirect bilirubin relating to Gilbert syndrome;
 - Serum creatinine > 1.6 mg/dL.
23. Known hypersensitivity to adalimumab or its excipients.
24. History of demyelinating disease (including myelitis) or neurologic symptoms suggestive of demyelinating disease.
25. History of invasive infection (e.g., listeriosis and histoplasmosis) or human immunodeficiency virus (HIV) or active TB.
26. Subject with any active viral infection that based on the investigator's clinical assessment makes the subject an unsuitable candidate for the study.

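### The Grade 3 or higher laboratory summary and its Fisher test ignore Baseline grade, so severe values already present before dosing and still present afterwards enter the counts

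*SAP*

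**What the plan says.** SAP 11.3 (Analysis of Laboratory Data) takes selected parameters that have Common Toxicity Criteria and summarises "frequencies and percentages of subjects with post baseline lab values that are Grade 3 or above". The between-group rule follows: "Comparisons of the percentage of subjects experiencing a value meeting the criteria between treatment groups will be performed using Fisher's exact tests". On reporting, it adds "Only P values ≤ 0.100 when rounded to three digits will be presented", which fits SAP 11.1, where safety differences are "evaluated using two-sided tests at the significance level of 0.100". SAP 11.1 also applies the safety analyses to the Any Adalimumab set as one group, with summary statistics only.

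Baseline enters the laboratory section in other outputs:

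- Mean changes from Baseline by visit.
- Normal-range tables: "Shift tables from baseline to the final value according to the normal range will be provided".
- For the four liver tests (SAP 11.3.1): "Shift tables showing shift from Baseline to maximum and final values will be presented using these five categories".
- A listing of subjects at Grade 3 or above: "For each of these subjects, the whole course of the respective parameter will be listed".

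SAP 6.0 defines a Baseline for each set. It is the last available value up to the first dose of study drug or, for laboratory data in the Any Adalimumab set, up to the first dose of adalimumab.

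Protocol 5.2.2, Exclusion 22, applies when "Screening laboratory and other analyses show any of the following abnormal results". Its numeric laboratory limits cover AST/ALT, WBC, total bilirubin and creatinine.

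**The concern.** A count of severe post-baseline values is normally read as what emerged after dosing. This one mixes two groups: subjects who became severe on study, and subjects who were severe at Baseline and stayed so. Only the first group tells the reader about the drug.

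The mixture is plausible in this population. Table 3 of the protocol measures hemoglobin, lymphocytes, neutrophils, platelets and albumin, among others, and none of these has a numeric entry limit. Low hematocrit adds to the CDAI score itself (Appendix C), so some anemia comes with the disease being enrolled. Azathioprine, 6-MP and methotrexate are allowed at entry, and the protocol itself gives leukopenia as an example of their toxicity.

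Two outputs are affected. In the randomised period, cases common to both arms dilute a real difference. In the Any Adalimumab summary there is no second arm, so persistent Baseline cases go straight into the percentage. That set's Baseline is reset at first adalimumab dose, planned at Week 4 for the placebo arm. A Grade 3 value that arose on placebo and persisted would therefore also be counted there.

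**Working it through.** **Step 1: is there a Baseline condition anywhere?** The places that could supply one, side by side:

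| Place | Rule | Conditions the Grade ≥ 3 count on Baseline? |
|---|---|---|
| SAP 11.3, CTC summary and Fisher test | Any post-baseline Grade ≥ 3 value | No |
| SAP 11.3, general shift tables | Baseline to final value, by normal range | No; separate output, neither by grade nor to worst value |
| SAP 11.3.1, liver shift tables | Baseline to maximum and final value | No; separate output, four tests only |
| SAP 6.0, analysis windows | All values used for shift and potentially clinically significant summaries | No |
| SAP 6.0, Baseline definition | Baseline available for each set | Makes a condition possible, does not impose one |
| SAP 11.2.1, adverse events | Onset or worsening after first dose required | Applies to adverse events only |
| Protocol 8.1.5 | Changes, shift tables, listings | No |

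The rule is as described. The plan states no figure on this point, so there is none to reproduce.

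**Step 2: effect on the randomised comparison (illustration).** From the documents: 100 subjects per arm (SAP 4.3) and two-sided 0.10 (SAP 11.1). Assumed, because the documents give no rates: new-onset Grade ≥ 3 in 6% versus 1%, and a share *b* with Grade ≥ 3 at Baseline that persists, equal in both arms.

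Reported rate = *b* + (1 − *b*) × new-onset rate. For *b* = 5%: adalimumab 0.05 + 0.95 × 0.06 = 10.7%; placebo 0.05 + 0.95 × 0.01 = 5.95%; ratio 10.7/5.95 = 1.8. Carried-over share of the count = *b*/reported rate: 5/10.7 = 47% and 5/5.95 = 84%. Power is exact Fisher, by full enumeration.

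| *b* | Reported, adalimumab vs placebo | Ratio | Carried-over share, adalimumab / placebo | Power as written | Power with Baseline cases removed |
|---|---|---|---|---|---|
| 0% | 6.0% vs 1.0% | 6.0 | 0 / 0 | 44% | 44% |
| 2% | 7.9% vs 3.0% | 2.6 | 25% / 67% | 32% | 43% |
| 5% | 10.7% vs 6.0% | 1.8 | 47% / 84% | 25% | 41% |
| 10% | 15.4% vs 10.9% | 1.4 | 65% / 92% | 19% | 40% |

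The last column drops Baseline cases from numerator and denominator (100, 98, 95 and 90 per arm). Keeping them in the denominator, as the fix below does, gives rates of (1 − *b*) × new. At *b* = 10% these are 5.4% versus 0.9%, with power 38% instead of 40%; the other rows do not change at this rounding. The ratio stays 6.0 either way.

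With assumed new-onset rates of 10% versus 2%, power as written is 69 / 57 / 46 / 34% for the same four values of *b*, against 69 / 68 / 66 / 67% with Baseline cases removed (63% at *b* = 10% if they stay in the denominator).

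**Step 3: false positives.** With no drug effect and equal Baseline shares of 2, 5 and 10%, exact Fisher type I error is 1.6, 4.2 and 6.2%, all below 10%.

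**Step 4: Any Adalimumab set.** Reported rate minus the rate of newly severe subjects = [*b* + (1 − *b*) × new] − (1 − *b*) × new = *b*. The excess is thus *b* percentage points whatever the new-onset rate, where *b* is now measured against that set's Baseline. It is slightly less if some of these subjects worsen from Grade 3 to 4, since those still count as new. If all 200 planned subjects are in the set, an assumed *b* of 2–10% is 4 to 20 subjects.

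**The case against.** **Eligibility screens out much of this.** Besides Exclusion 22, Exclusion 35 removes subjects whose screening laboratory results the investigator finds abnormal to a clinically significant degree, and Inclusion 8 requires otherwise good health, judged partly on the laboratory profile. Both bear on hemoglobin, lymphocytes and albumin. This stands as a reason to expect fewer cases. It does not close the gap: the judgement is not tied to a grade, and Screening may precede Baseline by up to 35 days.

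**The information is not hidden.** The whole-course listing lets a reader pick out prevalent cases one by one. That is true, but it corrects neither the percentage nor the p-value.

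**Counting every post-baseline value is the inclusive safety choice.** A strict worsening rule would drop a subject who starts at Grade 3, recovers and returns to Grade 3 on drug. This is a fair point, and it is why the fix needs a shift table as well as a new count.

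**Stronger readings a reader might infer.**

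- That the plan labels pre-existing disease as adalimumab toxicity. It does not: SAP 11.3 calls these post-baseline values and attributes nothing to the drug. Under Protocol 6.1.1.1 a laboratory abnormality is an adverse event only if further conditions are met, and it then falls under the onset-or-worsening rule.
- That the randomised comparison is biased towards a signal. Randomisation balances Baseline cases on average, and Step 3 shows no inflation of type I error.
- That a definite share of the reported counts is carried over. Any such share is a ratio of assumed rates, and a share built on four-week rates would not transfer to the Any Adalimumab table, where new events accumulate over the whole study.

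**Conclusion.** The point holds as a reporting weakness. SAP 11.3 counts and tests Grade 3 or higher laboratory values without regard to Baseline grade, and nothing elsewhere in either document supplies the condition. The consequences are lost sensitivity in the Week 0–4 comparison and a raised percentage in the single-group summary.

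The size cannot be derived from the documents: there are no rates, no grade cut-offs and no list of the selected parameters, so it is not even certain that hemoglobin, lymphocytes or albumin are among them. The figures above rest on assumed new-onset rates and on an assumed persistent Baseline share of 0–10%, equal in both arms. If that share is near zero, the effect is negligible. The comparison is a safety test without multiplicity adjustment, and no efficacy conclusion depends on it. Label: cheap improvement.

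**What to change.** In SAP 11.3, for both the summary and the Fisher test, count a subject when a post-baseline value is Grade 3 or above and of higher grade than the Baseline value of the analysis set in question (first study drug dose for the Safety set, first adalimumab dose for the Any Adalimumab set). Show subjects with a missing Baseline value separately.

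Add a shift table from Baseline to worst post-baseline CTC grade, so that subjects who stay at, or return to, the same severe grade remain visible. Keep the listing of all Grade 3 or higher values with the whole course.

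The cost is about one sentence in the SAP, one programming condition and one extra table. No new data are needed, because Baseline is already defined for both sets. The downside is that subjects unchanged at a severe grade leave the headline count and appear only in the shift table and listing.
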